2.1. Multiplicity Adjustment

Adjustment for multiple comparisons will not be employed in the analysis for this study.

3. Analysis Sets

Abbreviations: CDAI = Clinical Disease Activity Index; LDA = low disease activity; Q4W = every 4 weeks; Q12W = every 12 weeks; SC = subcutaneous.

Table KDAF.3.1. Treatment Groups and Comparisons for Each Study Period and Analysis Population

Study Period	Analysis	Treatment Group	Abbreviation	Inferential
	Population			Comparison
Double-blind, placebo- controlled treatment period (Period 2)	mITT Population Safety Population	Placebo SC Q4W ^a Peresolimab 100 mg SC Q4W Peresolimab 400 mg SC Q4W Peresolimab 1000 mg SC Q4W	PBO PER100Q4W PER400Q4W PER1000Q4W	PER100Q4W vs. PBO PER400Q4W vs. PBO PER1000Q4W vs. PBO
Double-blind treatment period Weeks 12 to 24 (Period 3A)	Maintenance Population	Placebo SC Q4W to Peresolimab 400 mg SC Q4W Placebo SC Q4W to Peresolimab 1000 mg SC Q4W Peresolimab 100 mg SC Q4W Peresolimab 400 mg SC Q4W Peresolimab 1000 mg SC Q4W	PBO/PER400Q4W PBO/PER1000Q4W PER100Q4W PER400Q4W PER1000Q4W	No Between-Treatment Comparison
Double-blind treatment period Weeks 24 to 60 (Period 3B)	Maintenance Primary Population	Peresolimab 400 mg SC Q4W Peresolimab 400 mg SC Q12W Peresolimab 1000 mg SC Q4W Peresolimab 1000 mg SC Q12W	PER400Q4W PER400Q12W PER1000Q4W PER1000Q12W	No Between-Treatment Comparison
	Maintenance Secondary Population	Peresolimab 400 mg SC Q4W Peresolimab 1000 mg SC Q4W	PER400Q4W PER1000Q4W	No Between-Treatment Comparison
	Maintenance Tertiary Population	Placebo SC Q4W to Peresolimab 400 mg SC Q4W Placebo SC Q4W to Peresolimab 1000 mg SC Q4W Peresolimab 100 mg SC Q4W	PBO/PER400Q4W PBO/PER1000Q4W PER100Q4W	No Between-Treatment Comparison
Combined Periods 2 and 3A (Weeks 0 to 24)	mITT Population	Placebo SC Q4W to Peresolimab 400 mg SC Q4W Placebo SC Q4W to Peresolimab 1000 mg SC Q4W Peresolimab 100 mg SC Q4W Peresolimab 400 mg SC Q4W Peresolimab 400 mg SC Q4W Peresolimab 1000 mg SC Q4W	PBO/PER400Q4W PBO/PER1000Q4W PER100Q4W PER400Q4W PER1000Q4W	No Between-Treatment Comparison
Treatment Period (combined Periods 2 and 3; Weeks 0 to 60)	Safety Population (for exposure table)	Peresolimab 100 mg SC Q4W Peresolimab 400 mg SC Q4W Peresolimab 1000 mg SC Q4W	PER100Q4W PER400Q4W PER1000Q4W PER400Q4W/Q12W	No Between-Treatment Comparison

Study Period	Analysis	Treatment Group	Abbreviation	Inferential
	Population			Comparison
	Safety	Peresolimab 400 mg SC Q4W to Peresolimab 400 mg SC	PER1000Q4W/Q12W	
	Population	Q12W	PBO/PER400Q4W	
	who Received	Peresolimab 1000 mg SC Q4W to Peresolimab 1000 mg	PBO/PER1000Q4W	
	at Least 1 Dose	SC Q12W	Total	
	of Peresolimab	Placebo SC Q4W to Peresolimab 400 mg SC Q4W		
		Placebo SC Q4W to Peresolimab 1000 mg SC Q4W		
		Total (Not applicable for exposure table)		
Posttreatment follow-up	Follow-up	Placebo SC Q4W	PBO	No Between-Treatment
period (Period 4)	Population	Peresolimab 100 mg SC Q4W	PER100Q4W	Comparison
		Peresolimab 400 mg SC Q4W	PER400Q4W	
		Peresolimab 400 mg SC Q12W	PER400Q12W	
		Peresolimab 1000 mg SC Q4W	PER1000Q4W	
		Peresolimab 1000 mg SC Q12W	PER1000Q12W	
		Total Peresolimab	Total PER	

Abbreviations: mITT = modified intent-to-treat; PBO = placebo; PER = peresolimab; Q4W every 4 weeks; Q12W = every 12 weeks; SC = subcutaneous.

^a Participants randomized to either Placebo SC Q4W to Peresolimab 400 mg SC Q4W or Placebo SC Q4W to Peresolimab 1000 mg SC Q4W will be combined as Placebo SC Q4W.

4. Statistical Analyses

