Participants randomly assigned to 400 mg or 1000 mg peresolimab at Week 0

Participants receiving 400 mg or 1000 mg peresolimab will continue their assigned dose and dosing frequency until Week 24. At Week 24, participants may be switched to every 12 weeks (Q12W) dosing following assessment of CDAI scores, unless they received rescue medication prior to Week 24.

Abbreviations: CDAI = Clinical Disease Activity Index; Q4W = every 4 weeks; Q12W = every 12 weeks.

- At Week 24 using the Visit 9 (Week 24) assessments, a participant does not achieve CDAI LDA
 - o These participants will receive permitted rescue therapy.
- For participants that achieved CDAI LDA at Week 24, those who do not maintain CDAI LDA for 2 consecutive visits after Week 24
 - o These participants will receive peresolimab Q4W and permitted rescue therapy.
 - If a participant is currently receiving peresolimab Q4W, they will continue receiving peresolimab Q4W.

• If a participant is currently receiving peresolimab Q12W, they will switch to peresolimab O4W.

[figure not shown]
Escape criteria after Week 24

A participant not achieving ≥20% improvement in both TJC and SJC at 2 consecutive visits after Week 24, while receiving rescue therapy, should be permanently discontinued from study intervention. Participants may continue in the study and receive additional standard of care therapies at the investigator's discretion.

Participation in an open-label extension study

If an open-label extension study is enrolling at the time the participant completes Visit 18 (Week 60), they will be given the opportunity to enroll in that study.

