1.2.1. Method of Assignment to Treatment

- 100 mg of peresolimab Q4W
- 400 mg of peresolimab Q4W
- 1000 mg of peresolimab Q4W
- placebo Q4W up to Week 12 followed by 400 mg of peresolimab Q4W, and
- placebo Q4W up to Week 12 followed by 1000 mg of peresolimab Q4W.

Participants who are randomized to either peresolimab 400 mg Q4W or peresolimab 1000 mg Q4W at Week 0 and meet CDAI \leq 10 at Week 24 will be randomly assigned to either Q4W or Q12W in the same dose level with a 1:1 ratio. Participants will be stratified by

• CDAI <2.8 vs 2.8 < CDAI <6 vs CDAI >6 at Week 24.

2. Statistical Hypotheses

The primary objective is to demonstrate that peresolimab is superior to placebo in achieving ACR20 at Week 12. Thus, the null hypothesis to be tested in relation to the primary estimand is:

There is no difference between peresolimab and placebo when evaluating the proportion of study participants with moderately-to-severely active RA achieving ACR20 at Week 12.

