4.9. Changes to Protocol-Planned Analyses

There is no change to protocol-planned analyses.

5. Sample Size Determination

Approximately 420 participants CCI

- 100 mg of peresolimab Q4W
- 400 mg of peresolimab Q4W
- 1000 mg of peresolimab Q4W
- Placebo to 400 mg of peresolimab Q4W, or
- Placebo to 1000 mg of peresolimab Q4W.

CCI

- At Week 12, the 100 mg peresolimab treatment group will have a sample size of approximately 60 participants, and the 400 mg and 1000 mg peresolimab treatment groups will each have a sample size of approximately 120 participants.
- At Week 12, the placebo group will have a sample size of approximately 120 participants.

6. Supporting Documentation

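### The Weeks 0 to 60 safety columns at 400 mg and 1000 mg are split by Week 24 status, so the Q4W/Q12W columns cannot show an event that ended treatment before Week 24

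*SAP*

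**What the plan says.** **Regimen before Week 24.** SAP Section 1.2: "Participants receiving 400 mg or 1000 mg peresolimab will continue their assigned dose and dosing frequency until Week 24". Both doses are given Q4W over that time, so nobody is on Q12W before Week 24.

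**Route to Q12W.** SAP Section 1.2.1 limits the second randomisation to 400 mg and 1000 mg participants with CDAI of 10 or less, who "at Week 24 will be randomly assigned to either Q4W or Q12W in the same dose level with a 1:1 ratio". Section 1.2 excludes anyone rescued before Week 24. It also returns Q12W participants to Q4W if they lose low disease activity at two consecutive visits.

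**Columns for Weeks 0 to 60.** The Treatment Period rows of Table KDAF.3.1 (SAP Section 3) list plain Q4W groups at each dose. They also list the sequences "Peresolimab 400 mg SC Q4W to Peresolimab 400 mg SC" Q12W and "Peresolimab 1000 mg SC Q4W to Peresolimab 1000 mg" SC Q12W, the two placebo-switch groups and a total. The inferential column plans no between-treatment comparison. The SAP version history says these groups were updated in Version 3 for selected safety analyses.

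**Outputs over that period.** By treatment arm over the Treatment Period, the SAP plans hypersensitivity frequencies (Section 4.6.2.2), Kaplan-Meier time to first infection counted from the first injection (4.6.2.4), and malignancy frequencies and rates per 100 patient-years (4.6.2.5).

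**Period 3B.** Section 4.6 summarises Weeks 24 to 60 by the treatment assigned at Week 24, but combines the Maintenance Primary, Secondary and Tertiary Populations.

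**The concern.** Over Weeks 0 to 24 all participants at a given dose are on the same regimen. The table nevertheless divides their events and follow-up into two columns, using a response and a treatment-retention status that are known only at Week 24.

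Two distortions follow. First, a participant in a Q4W/Q12W column must have remained on treatment for 24 weeks. An event that ends treatment cannot occur in that stretch, yet the time still counts in a patient-year denominator. For a Week 60 completer it is 24/60 = 40% of the person-time. Second, the column holds only responders, while nonresponders and rescued participants at the same dose all go to Q4W.

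The study is meant to inform dosing frequency, and its safety analysis is wholly descriptive, so adjacent columns are what a reader will compare. The events exposed include planned outputs. Protocol Section 7.1 lists systemic hypersensitivity related to study intervention, and active or untreated malignancy, among the grounds for permanent discontinuation. SAP Section 4.6.2 names hypersensitivity and malignancy as adverse events of special interest.

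**Working it through.** **The plan's own figure.** SAP Section 5 gives "Approximately 420 participants". Its arms are 60 (100 mg), 120 (400 mg), 120 (1000 mg) and 120 (pooled placebo): 60 + 120 + 120 + 120 = 420, which agrees. The visible text gives no discontinuation rate and no Week 24 response rate, so the size below rests on assumed ranges.

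**Inputs, one dose arm**
- N = 120 (SAP Section 5).
- d = probability of stopping for an AE before Week 24: 3%, 5% or 10% (assumed).
- q = share of those reaching Week 24 who are eligible for re-randomisation: 20%, 35% or 50% (assumed).
- Half of the eligible go to Q12W (SAP Section 1.2.1).
- Constant hazard, the same for everyone, with no regimen effect (assumed).

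**Formulas**
- Risk over Weeks 24 to 60: p = 1 − (1 − d)^(36/24).
- Size of the Q4W/Q12W column: nQ = N(1 − d)q/2. Size of the Q4W column: N − nQ.
- Q4W/Q12W proportion: p, because nothing can be counted there before Week 24.
- Q4W proportion: [N·d + (N(1 − d) − nQ)·p] / (N − nQ).

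**Worked case, d = 5%, q = 35%**
- p = 1 − 0.95^1.5 = 7.4%.
- nQ = 120 × 0.95 × 0.35/2 = 19.95; the Q4W column has 100.05.
- Q4W events = 6 + (114 − 19.95) × 0.0741 = 12.96; 12.96/100.05 = 13.0%.
- Ratio = 7.4/13.0 = 0.57, where the truth is 1.

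**Expected AE discontinuation, Weeks 0 to 60, q = 35%**

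| d | Q4W/Q12W column | Q4W column | Whole Week 0 arm, 1 − (1 − d)^(60/24) |
|---|---|---|---|
| 3% | 4.5% | 7.9% | 7.3% |
| 5% | 7.4% | 13.0% | 12.0% |
| 10% | 14.6% | 24.8% | 23.2% |

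Over all nine combinations of d and q, the ratio of proportions runs from 0.54 (d = 3%, q = 50%) to 0.61 (d = 10%, q = 20%). With each column's full follow-up as denominator, the ratio of rates per patient-year runs from 0.51 to 0.57.

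**An event unrelated to stopping or response.** Take a 30% risk over 60 weeks, independent of discontinuation, with d = 10% and q = 35%.
- Weekly hazards: μ = −ln(0.7)/60 = 0.00594 for the event; λ = −ln(0.9)/24 = 0.00439 for stopping.
- Whole arm: μ/(μ + λ) × (1 − e^(−60(μ + λ))) = 26.6%.
- Q4W/Q12W column: (1 − e^(−24μ)) + e^(−24μ) × μ/(μ + λ) × (1 − e^(−36(μ + λ))) = 28.8%.
- Q4W column: (120 × 0.2658 − 18.9 × 0.2879)/101.1 = 26.2%.

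The crude percentage is now slightly higher for Q12W, because that column is guaranteed at least 24 weeks of follow-up.

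**Starting at Week 24 among the re-randomised only.** Both groups have expected risk p: 4.5% v 4.5%, 7.4% v 7.4% or 14.6% v 14.6%. The ratio is 1.00.

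**The case against.** The strongest reply has four parts.

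1. **No comparison is planned.** The row is descriptive, and Week 0 counts can be recovered by adding the two columns at a dose. This stands as far as it goes: no test or planned estimate is biased. Adding columns does not recover the Kaplan-Meier curves, however, and the display still invites a Q4W against Q12W reading.

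2. **Safety is also summarised by period.** Periods 2 and 3A follow the Week 0 assignment and Period 3B starts at Week 24. This covers early events by original dose. It does not give a clean frequency contrast. In Period 3B the Q4W groups combine re-randomised responders with the other 400 mg and 1000 mg participants, so the selection on response remains.

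3. **AE discontinuation is not expressly assigned to the Weeks 0 to 60 row.** This stands. The figures above illustrate the mechanism for events that end treatment. The outputs that the SAP does tie to the Treatment Period, such as hypersensitivity and malignancy, are affected to the extent that such events stop treatment or accompany poor response.

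4. **The assignment rule is inferred.** This stands too. It is read from the column labels and from the Week 24 rule in Section 4.6, which sits in the Period 3B text. Wording not shown in the public copy may state it.

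A reader might also infer that all early discontinuations land in the Q4W columns. They do not. A Q12W participant who stops after Week 24 stays in the Q12W column, and the 100 mg and placebo-switch columns are fixed at Week 0. Nor does Q12W look safer on every outcome, as the 28.8% v 26.2% example shows.

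**Conclusion.** The concern holds in a limited form. At 400 mg and 1000 mg, the Weeks 0 to 60 safety columns condition on retention and response at Week 24. With no true regimen effect this favours Q12W for death, AE discontinuation and events tied to stopping treatment or to poor response.

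For AE discontinuation the ratio of proportions is about 0.54 to 0.61. That rests on the assumed 3% to 10% stopping before Week 24, 20% to 50% eligible, a constant hazard and the inferred column rule. For events unrelated to stopping, crude percentages may move slightly in the opposite direction, so the documents do not support a general claim that Q12W is made to look safer.

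Primary efficacy is untouched and no formal comparison is affected. The harm is a misleading side-by-side display on a question that the study is meant to inform, and the visible text plans no safety summary of Q4W and Q12W restricted to the re-randomised participants. The change should be made.

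**What to change.** - Summarise Weeks 0 to 60 safety by Week 0 arm. The exposure table may keep the sequence columns, where they usefully show time on each regimen.
- Present Q4W and Q12W safety side by side only from Week 24, with Week 24 as time zero, and only in the re-randomised participants. The Maintenance Primary Population in Table KDAF.3.1 already has the four groups needed.
- State the rule that assigns participants to columns, and how events after a return from Q12W to Q4W are attributed.

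No new data are needed. The cost is one additional safety table with small groups: under the assumptions above, about 11 to 29 participants per regimen at each dose (nQ at its extremes is 10.8 and 29.1).

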4.1. General Considerations

Statistical analysis of this study will be the responsibility of sponsor or its designee. A detailed SAP describing the statistical methodologies will be developed by the sponsor or its designee.

Handling of missing, unused, and spurious data are addressed prospectively in the overall statistical methods described in the protocol and in the SAP, where appropriate. Adjustments to the planned analyses are described in the final clinical study report (CSR).

Baseline for the Treatment Period is defined as the last nonmissing assessment on or prior to the date of the first injection of study treatment for efficacy, unless otherwise specified. In most cases, this will be the measure recorded at Week 0 (Visit 2). For safety analyses, baseline will be defined by period as last nonmissing assessment prior to the first dosing of each period. The Treatment Period starts after the first injection and ends on date of Visit 18 (Week 60) or early discontinuation (ED). Any assessment collected after the first injection is defined as postbaseline for the Treatment Period. If ET visit does not occur, last injection date will be considered as the end of the treatment period. Baseline for safety analysis of the Posttreatment Follow-Up period (Period 4) is defined as the last nonmissing assessment prior to entering Period 4, that is date of Visit 18 (Week 60) or ET.

During this study, data issue was identified for the collection date/time of the electronic clinical outcome assessments (eCOA). Same analysis visit was assigned to eCOA assessment with different collection date than the corresponding visit date. Because of this, study team came up with a method to handle this data issue, which is the analysis visit numbers for electronic clinical outcome assessments (eCOA) data will be assigned based on the actual visit date recorded in the electronic case report form (eCRF). If the eCOA assessment date is within +/- 3 days window of the actual visit, then the analysis visit number of the eCOA assessment will be assigned as the actual visit number. If the eCOA assessment date is outside +/- 3 days window of all the actual visits, then the analysis visit of the eCOA assessment will be considered as unscheduled visit. The eCOA data will be used for the analysis only when the analysis visit number of the eCOA assessment is identical to the visit number captured in the eCOA system.

For analyses in Period 2, participants randomized to either Placebo subcutaneous (SC) Q4W to Peresolimab 400 mg SC Q4W or Placebo SC Q4W to Peresolimab 1000 mg SC Q4W will be combined as Placebo SC Q4W.

Dichotomous efficacy endpoints including the primary endpoint during Period 2 will be analyzed using a CCI

Period 2, an estimate of the treatment difference with corresponding Wald 95% confidence interval (CI), the odds ratio with corresponding Wald 95% CI and p-value will be presented. Each treatment group will be compared to Placebo SC Q4W.

Continuous efficacy endpoints, which are planned to be collected at >1 postbaseline timepoints during Period 2 according to the SoA, will be analyzed using mixed-effect model for repeated measures (MMRM) analysis. The MMRM model will include:

- treatment, stratification factors, baseline value, visit and treatment-by-visit interaction in the model as fixed factors, and
- participant as a random factor.

The least squares (LS) mean for each treatment group along with the estimate of the difference between each treatment group with Placebo SC Q4W, standard error (SE), p-value, and the 95% CIs will be reported at each visit along with p-values.

The covariance structure to model the within-participant errors will be unstructured. If the unstructured covariance matrix results in a lack of convergence, the heterogeneous Toeplitz covariance structure, followed by the CCI, will be used.

The CCI will be used to estimate the denominator degrees of freedom.

Type III sums of squares for the LS means will be used for the statistical comparison. The 95% CI will also be reported.

When continuous efficacy endpoints are analyzed using CCI , the model will include treatment group, stratification factors, and baseline value as covariates. Type III sums of squares for the LS means will be used for statistical comparison between each treatment group and Placebo SC Q4W. The LS mean difference, SE, p-value, and 95% CI, unless otherwise specified, will also be reported.

Dose response modeling will be performed on the primary, and other core efficacy endpoints, if deemed necessary, to assist in dose selection decisions. More details will be provided in Section 4.2.

Data collected after initiation of rescue or prohibited medication use will be handled according to the specified estimand strategy for efficacy analysis. Such data, unless otherwise noted, will be excluded from efficacy analyses, considered as missing, and handled according to a missing data imputation method as specified.

Missing data will be handled separately from estimand strategy. After intercurrent events related to study intervention are accounted for according to an estimand strategy specified in Section 1.1, any remaining missing data will be handled using the following missing data imputation methods:

• Nonresponder imputation (NRI):

When NRI is applied, participants with missing data will be considered as nonresponders regardless of whether they have at least 1 postbaseline data.

• LOCF:

When LOCF is applied, the last nonmissing observation up to Week 24 will be carried to the corresponding time point for evaluation. For participants who initiated rescue therapy, the last nonmissing observation prior to the initiation of rescue therapy will be carried forward. For randomized participants without any postbaseline observation, missing data will not be imputed.

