4.6.3. Clinical Laboratory Evaluation

All numerical laboratory tests for serum chemistries, fasting lipids, hematology, rheumatoid factor (RF) and anti-CCP antibodies, CRP, and ESR will be summarized by treatment arm for observed and change from baseline values during the Treatment Period.

Urinalysis will appear in data listings.

Summary of B-cells, immunoglobulins (Igs), and immunogenicity tests are described in the subsections below.

Change from baseline in laboratory tests will be summarized for patients who have both a baseline and at least postbaseline result.

Change from the minimum value on or prior to the date of the first injection of study treatment to the minimum value during the Treatment Period in laboratory tests will be summarized for patients who have both a baseline and at least 1 postbaseline result. Similarly, change from the maximum value on or prior to the date of the first injection of study treatment to the maximum value during the Treatment Period in laboratory tests will be summarized for patients who have both a baseline and at least 1 post-baseline result. Scheduled visits, unscheduled visits, and repeat measurements will be included.

The frequency and percentage of patients with treatment-emergent abnormal, high, or low laboratory results at any time will be summarized. Similarly, the frequency and percentage of patients with treatment-emergent abnormal, high, or low laboratory results will be summarized. A treatment-emergent abnormal result is defined as a change from normal at all baseline visits to abnormal at any time during the Treatment Period. A treatment-emergent high result is defined as a change from a value less than or equal to the high limit at all baseline visits to a value greater than the high limit at any time during the Treatment Period. A treatment-emergent low result is defined as a change from a value greater than or equal to the low limit at all baseline visits to a value less than the low limit at any time during the Treatment Period. For each laboratory test, only patients who were normal (that is, less than or equal to the high limit for treatment-emergent high, or greater than or equal to the low limit for treatment-emergent low) at all baseline visits and who have at least 1 nonmissing postbaseline result will be included in the denominator when computing the percentages of patients with treatment-emergent abnormal,

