high, or low results. Scheduled visits, unscheduled visits, and repeat measurements will be included. Covance Reference Ranges will be used to define the low and high limits. Listing of significant lab test abnormalities will be provided.

Shifts from baseline to maximum postbaseline result during the Treatment Period for alanine aminotransferase (ALT), aspartate aminotransferase (AST), alkaline phosphatase (ALP) and total bilirubin will be provided for the following categories:

- ALT, AST; \leq 1 × upper limit of normal (ULN), >1 to <3 × ULN, \geq 3 to <5 × ULN, \geq 5 to <10 × ULN, and \geq 10 × ULN
- ALP; $\leq 1 \times ULN$, ≥ 1 to $\leq 1.5 \times ULN$, ≥ 1.5 to $\leq 2 \times ULN$, $\geq 2 \times ULN$
- Total bilirubin; $\le 1 \times ULN$, >1 to $<1.5 \times ULN$, ≥ 1.5 to $<2 \times ULN$, $\ge 2 \times ULN$

Lab Evaluation of Drug-Induced Serious Hepatotoxicity plot will be created with maximum postbaseline ALT/AST divided by ULN vs. maximum postbaseline total bilirubin divided by ULN.

Hematologic changes will be defined based on clinical laboratory assessments. Common Terminology Criteria for Adverse Events (CTCAEs) will be applied for selected laboratory tests. Shifts from maximum baseline to maximum postbaseline result will be provided by treatment periods for the categories in Appendix 11 (Section 6.11).

Shift tables from maximum baseline to maximum postbaseline for lipid effects that include total cholesterol and triglycerides will be categorized based on NCEP levels in Appendix 11 (Section 6.11) and summarized by treatment periods.

Shift table from maximum baseline to maximum postbaseline for renal function that includes elevated creatinine will be categorized based on CTCAE in Appendix 11 (Section 6.11) and summarized by treatment periods.

Scheduled visits, unscheduled visits, and repeat measurements will be included.

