4.6.4. Pharmacodynamics

4.6.4.1. Flow Cytometry

For flow cytometry panel, the absolute count and relative count (that is, as a percentage of the total lymphocyte population) will be summarized by treatment arm for baseline and all postbaseline visits during the Treatment Period using descriptive statistics.

The change from baseline and the percent change from baseline to each postbaseline visit during the Treatment Period will be summarized for absolute and relative count. Note that the baseline count is defined as the average of the nonmissing results on or prior to the date of the first injection of blinded study treatment, unless 1 is missing, in which case the nonmissing result will be used. Unscheduled and repeated measurements will be included.

In addition, the mean absolute and relative counts during the Treatment Period will be presented graphically over time (in weeks) by treatment arm. Similarly, the mean percentage change from

baseline in absolute and relative counts will be presented graphically over time (in weeks) by treatment arm.

A by-patient listing of cytometry cell counts during the Treatment Period will be provided.

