4.6.4.2. Serum Immunoglobulin Levels and Cytokines

Serum Ig levels, including IgA, IgG, and IgM, and cytokines will be summarized by treatment arm for baseline, postbaseline visits, and both change from baseline and percent change from baseline to each postbaseline visit. Baseline is defined as the last nonmissing result on or prior to the date of the first injection of study treatment.

For each parameter, the mean percentage change from baseline over time (in weeks) will be summarized graphically by treatment arm.

Shift tables will be produced showing the frequency and percentage of patients with a minimum postbaseline result during the Treatment Period in each relevant category, by treatment arm and baseline result. Such shift tables will be produced for the following parameters and categories:

- IgA; <LLN to ≥ 0.35 g/L, and <0.35 g/L
- IgG: <LLN to \ge 2.82 g/L, and <2.82 g/L
- IgM: <LLN to \ge 0.20 g/L, and <0.20 g/L

A by-patient listing of serum Ig levels and cytokines during the Treatment Period will be provided.

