4.6.5. Vital Signs and Other Physical Findings

Vital signs and physical characteristics to be summarized include temperature, sitting heart rate, sitting blood pressure (systolic and diastolic), weight, and body mass index (BMI). Vital signs and physical characteristics will be summarized by treatment arm for baseline, postbaseline visits, and change from baseline to postbaseline visits.

Change from baseline in vital signs and physical characteristics will be summarized for patients who have both a baseline and at least 1 postbaseline result. Baseline is defined as the last nonmissing result on or prior to the date of the first injection of study treatment for each period.

Change from the minimum value on or prior to the date of the first injection of study treatment to the minimum value during the Treatment Period in vital signs and physical characteristics will be summarized for patients who have both a baseline and at least 1 postbaseline result. Similarly, change from the maximum value on or prior to the date of the first injection of study treatment to the maximum value during the Treatment Period in vital signs and physical characteristics will be summarized for patients who have both a baseline and at least 1 postbaseline result. Scheduled visits, unscheduled visits, and repeat measurements will be included.

The percentages of patients with treatment-emergent high or low vital signs and physical characteristics at any time during the Treatment Period will be summarized. Similarly, the percentages of patients with treatment-emergent high or low vital signs and physical characteristics will be summarized. A treatment-emergent high result is defined as a change from a value less than the high limit at all baseline visits to a value greater than or equal to the high limit at any time during the Treatment Period. A treatment-emergent low result is defined as a change from a value greater than the low limit at all baseline visits to a value less than or equal to the low limit at any time during the Treatment Period. For each vital sign and physical characteristic, only patients who were normal (that is, less than the high limit for treatment-emergent high or greater than the low limit for treatment-emergent low) at all baseline visits and who have at least 1 nonmissing postbaseline result will be included in the denominator when computing the percentages of patients with treatment-emergent high or low results. Scheduled

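### Vital-sign and weight baselines are reset at Weeks 12 and 24, so most Period 3 displays give no by-visit change from the value before peresolimab

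*SAP*

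**What the plan says.** The general rule in SAP 4.1 is: "For safety analyses, baseline will be defined by period as last nonmissing assessment prior to the first dosing of each period". SAP 4.6.5 restates it for vital signs and physical characteristics, which include weight and BMI: "Baseline is defined as the last nonmissing result on or prior to the date of the first injection of study treatment for each period". The planned by-visit display there is "summarized by treatment arm for baseline, postbaseline visits, and change from baseline to postbaseline visits".

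SAP 4.6 summarises safety by treatment period. SAP 1.2 defines Period 2 as the first 12 weeks, Period 3A as Weeks 12 to 24 and Period 3B as Weeks 24 to 60. It also starts the placebo arms on 400 mg or 1000 mg peresolimab at Week 12.

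Two other subsections of SAP 4.6 use a different anchor for by-visit change. For immunoglobulins and cytokines (4.6.4.2), "Baseline is defined as the last nonmissing result on or prior to the date of the first injection of study treatment". For flow cytometry (4.6.4.1), "the baseline count is defined as the average of the nonmissing results on or prior to the date of the first injection".

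The Version 2 change log in the SAP gives the reason for the period rule: summarising safety by period is said to require a baseline for each period.

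**The concern.** Weeks 12 to 60 are where longer-term vital-sign and weight safety is read. In arms on peresolimab since Week 0, the Period 3 baselines are taken on drug. A rise in blood pressure or weight that develops by Week 12 and then persists gives a Period 3 change near zero. A slow drift is cut into three segments, each starting again from zero.

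In Period 3A the same effect would appear in full for the placebo-switch arms, because their Week 12 baseline precedes peresolimab. Two columns under the same change heading would then measure different things. A reader could take the difference for a safety contrast between arms when it comes from the anchor.

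The stated reason for the rule does not force this result. Results can be displayed by period and still be anchored to a pre-drug value.

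**Working it through.** The plan states no figure to reproduce. The check traces the baseline rule arm by arm and then bounds what the change column can show.

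**Weeks on peresolimab at each baseline** (SAP 1.2, 4.1, 4.6.5)

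| Arms | Period 2 | Period 3A | Period 3B |
|---|---|---|---|
| 100, 400, 1000 mg from Week 0 | 0 | 12 | 24 |
| Placebo-switch | 0 (on placebo in this period) | 0 | 12 |

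By-visit change from the pre-peresolimab value is therefore missing for the continuing arms in 3A and 3B, and for the switch arms in 3B. It is present for the switch arms in 3A.

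**Planned numbers** (SAP 5)

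Continuing arms: 60 + 120 + 120 = 300, and 300/420 = 71%. Placebo-switch arms: 120/420 = 29%. These are planned sizes, before any dropout.

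**Share of the change since first dose that the period table shows**

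Assume F(t) is the mean effect after t weeks on peresolimab, with F(0) = 0, no reversal, no acceleration (concave) and a constant regimen. Concavity gives F(12) ≥ F(24) × 12/24, and likewise for the other pairs.

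- Continuing, Week 24: [F(24) − F(12)]/F(24), at most 12/24 = 50%.
- Continuing, Week 60: [F(60) − F(24)]/F(60), at most 36/60 = 60%.
- Switch, Week 24: [F(12) − F(0)]/F(12) = 100%.
- Switch, Week 60 (48 weeks on drug): [F(48) − F(12)]/F(48), at most 36/48 = 75%.

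Except for the 100% case, the lower bound is 0%, reached when the effect is complete within 12 weeks of the first dose. The upper bound is linear drift.

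Illustration with F(t) = 1 − exp(−t/τ), where τ is assumed:

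| τ (weeks) | Continuing, Week 24 | Continuing, Week 60 | Switch, Week 60 |
|---|---|---|---|
| 4 | 5% | 0% | 5% |
| 12 | 27% | 13% | 36% |
| 24 | 38% | 31% | 54% |
| 48 | 44% | 45% | 65% |

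**Can the reader rebuild the change by adding tables?**

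Only roughly. SAP 4.6 uses the Safety Population for Period 2 and the Maintenance Population for 3A. The SD of a summed change is √(s₁² + s₂² + 2ρs₁s₂). With s₁ = s₂ = s it lies anywhere from 0 to 2s, because ρ is not displayed.

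**Threshold table in SAP 4.6.5**

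The weight limit is a change of at least 7% from baseline, and the blood-pressure and heart-rate limits also include a change from baseline. As an assumed example, a 4% weight gain in each of the three periods gives 1.04³ = 1.125, a cumulative gain of 12.5%. Against a baseline reset each period, no single period reaches 7%.

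**The case against.** The period baseline is a reasoned choice. At Week 24, participants on 400 or 1000 mg with CDAI of 10 or less are re-randomised to Q4W or Q12W (SAP 1.2.1), and change from Week 24 is the natural quantity for those groups. Table KDAF.3.1 plans no between-treatment comparison in Period 3. This stands, and is why the existing tables should be kept.

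Pre-drug information is also planned elsewhere. SAP 4.6.5 shows baseline and postbaseline values by visit, changes from the minimum and maximum on or before the first injection, treatment-emergent high and low results, and by-patient listings. A sustained shift would appear in the levels. This stands too, and it limits the harm. It does not close the gap. The minimum and maximum changes have no visit dimension, and differences between displayed means give no paired change or its SD. In Period 3B the groups are also re-formed by Week 24 assignment, so the Week 0 mean of the whole 400 mg arm is not the Week 0 mean of its Q4W or Q12W subgroup.

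Table KDAF.3.1 has a combined Weeks 0 to 60 safety row, and a by-visit table anchored at Week 0 could be produced from it. The Version 3 change log assigns that row only to selected analyses, and vital signs by visit are not named.

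The contrast with other displays is limited. Flow cytometry and immunoglobulins sit under Pharmacodynamics. Laboratory change "will be summarized by treatment arm for observed and change from baseline values during the Treatment Period" has no baseline definition of its own, so it is not clear evidence of a pre-drug anchor.

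Finally, vital signs are not among the adverse events of special interest (SAP 4.6.2), and Protocol 2.3.1 names no vital-sign risk. That supports a low severity.

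**Conclusion.** The point holds as a minor one. By-visit vital-sign and weight change from the pre-peresolimab value is not stated for the continuing arms in Period 3 (about 300 of 420 planned) or for the switch arms in Period 3B. The Period 3A display also mixes on-drug and off-drug baselines. The arm tracing follows directly from the text. The 0–50%, 0–60% and 0–75% shares are structural bounds and do not predict any effect. They assume a concave effect on a constant regimen, which fails for participants moved to Q12W or given rescue therapy from Week 24, and they describe only the change column.

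Three stronger readings are not supported.

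- A reader might infer that no Period 3 display gives change from a pre-peresolimab value. The Period 3A display does so for both switch arms.
- A reader might infer that a safety signal would be lost. The observed values, minimum and maximum changes and listings argue against that.
- A reader might extend the point to the hematology, lipid and creatinine shifts, where "Shifts from maximum baseline to maximum postbaseline result will be provided by treatment periods for the categories in Appendix 11". The maximum baseline is not defined there, but the same section describes "change from the maximum value on or prior to the date of the first injection of study treatment to the maximum value", which favours a pre-first-injection reading.

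One related matter is unsettled. The treatment-emergent rule in SAP 4.6.5 refers to all baseline visits, which suggests a pre-treatment anchor, but the explicit baseline definition in that section is by period.

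**What to change.** In SAP 4.6.5:

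- Keep the period-baseline tables.
- Add by-visit change in vital signs and weight for Periods 3A and 3B against the last value before the first peresolimab dose: Week 0 for arms randomised to peresolimab, Week 12 for placebo-switch arms.
- State that the change thresholds, including weight change of at least 7%, use a pre-treatment anchor when assessed over the Treatment Period.

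No extra laboratory shift tables are needed for this point.

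The cost is a few sentences in the SAP, one derived baseline flag and a few extra tables. No new data are collected and no planned output is removed. The downside is a slightly longer table package.
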